2.0 Proposed Research

Hypothesis:

Women with MS experience worsening of fatigue, as self-reported by MFIS, during menstruation compared to other times during their menstrual cycles.

Design:

Prospective observational self-enrolled study on mobile app.

Setting:

online, app reporting

Subjects:

Females living with MS, who experience menstruation.

Inclusion Criteria:

Participants are required to meet the following criteria:

- Females with diagnosed MS by 2017 McDonald criteria ¹ (biologically sex-based, any gender as long as not on hormonal gender-enhancing therapy)
- ages 16+, still experiencing menstruation with cycles of 23 to 36 days spacing
- have entered menarche, are experiencing menstrual cycles, and have not yet entered menopause
- participants may utilize hormonal contraceptive methods, such as oral contraceptive methods or hormonal IUDs
- English-speaking
- Willing to provide informed consent, mature minors will provide informed consent, their physician will determine whether their level of maturity is appropriate to participate in the study and complete consent as a mature minor
- Have the ability to complete questionnaires and operate the app

Exclusion Criteria:

People will be excluded as per the following criteria:

- diagnosed with other CNS inflammation disorders than MS
- male or intersex individuals, given the inclusion criteria of requiring a uterus
- females < 15 years of age
- females who have not started menstruation
- females who have stopped menstruation due to menopause or hysterectomy

- pregnant or postpartum women x 1 year after delivery and/or people who currently breastfeeding
- are unable to provide informed consent
- are unable to complete questionnaires and operate the app

Randomization:

n/a

Questionnaires:

Baseline:

- **PDDS** – single scale (physical disability measure) Patient Determined Disease Steps ⁴³
- **Full MFIS** – Modified Fatigue Impact Scale (21 point scale) – fatigue ^{2, 8, 9}
- **HADS** (anxiety & depression) – Hospital Anxiety & Depression Scale (14 items)⁵
- **PHQ9** – Patient Health Questionnaire (depression & anxiety) (9 items)^{44, 45}
- **MSNQ** (cognition) (15 item)¹¹⁻¹³
- **Mini Cope** (coping) (12 item)⁴⁶
- **Pittsburgh sleep quality index** (sleep quality) (24 items)⁴⁷
- **the SymptoMScreen** (12 item) (walking, hand function/dexterity, spasticity & stiffness, bodily pain, sensory symptoms, bladder control, fatigue, vision, dizziness, cognition function, depression, anxiety)^{7, 42}

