Taylor et al completed a pilot study, published in 2023, on menstrual cycle and fatigue symptoms in eumenorrheic women living with MS. There was a suggestion of less fatigue in the perimenstrual period compared to the luteal portion of the cycle, and less fluctuation in symptom severity over the cycle for women on continuous hormonal oral contraception. There was a lot of difficulty recruiting for this study with over 200 women contacted and 70 enrolled and 47 providing more than 4 weeks of data for a 6 month period.⁴² Despite the challenges faced by these authors, and anticipating a 20% dropout, we plan to try to recruit a maximum of 300 participants over 2 years. There are no substantial prior studies to base the sample size calculation upon.

Analytical Plan:

We will calculate summary statistics for primary and secondary outcomes across different menstrual cycle phases. We will conduct hypothesis tests (e.g., t-tests, ANOVA) to determine if there are statistically significant crude differences in MS symptom severity or relapse rates among different menstrual cycle phases and explore the relationship between the timing of the menstrual cycle and MS symptom severity using correlation coefficients (e.g., Pearson's correlation). We will perform regression analysis to identify any potential predictors of MS symptom severity, including menstrual cycle phase, age, duration of MS, and other relevant covariates and stratify the analysis by age groups to explore for effect modification by reproductive stage of youth, early adulthood (reproductive years) and later adulthood (peri-menopause), respectively defined as participants < 20 years old, 20 to 40 years old, > 40 years old. We will control for potential confounding variables, such as medication use, comorbidities, and lifestyle factors, in these adjusted models. Finally, we will perform sensitivity analysis to assess the robustness of the results by varying assumptions or analytical methods. Finally, we will provide descriptive measures of baseline characteristics/demographics.

Feasibility:

This study will be carried out through the reciprocal ethics process at the Universities of Alberta and Calgary. Each MS Clinic at each clinic follows about 5000 PwMS in Alberta. MS affects 3 women to every man, with average onset between ages 20 to 40. Therefore, both clinics see many women with MS who are at ages who experience menarche.

Timelines:

2 years, each site to recruit 150 participants maximum

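### Effect modification by age is explored only through three separate age bands; no phase-by-age interaction is named, so nothing tests whether the phase effect differs by age

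*Combined protocol and SAP*

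**What the plan says.** Section 2.0, Analytical Plan, proposes a regression of symptom severity on predictors "including menstrual cycle phase, age, duration of MS, and other relevant covariates". It will then "stratify the analysis by age groups to explore for effect modification by reproductive stage". The bands are "respectively defined as participants < 20 years old, 20 to 40 years old, > 40 years old"; the first stands for youth, the second for the reproductive years and the third for peri-menopause. The section names no product of phase and age, no test of heterogeneity between bands, no minimum band size and no multiplicity rule.

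Three other passages bear on the bands:

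- **Inclusion Criteria (opening synopsis and Section 2.0).** Entry requires "ages 16+, still experiencing menstruation with cycles of 23 to 36 days spacing". Participants must also "have entered menarche, are experiencing menstrual cycles, and have not yet entered menopause". Peri-menopause is neither defined nor excluded.
- **Questionnaires, Baseline.** Age, cycle length and type of contraception are collected. No peri-menopausal staging is listed.
- **Feasibility.** The only information on age is that "MS affects 3 women to every man, with average onset between ages 20 to 40". No age distribution of the clinics or of the expected sample is given.

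**The concern.** Effect modification is a statement about a difference between phase effects. Estimating the phase effect separately in each band, with age otherwise only a main effect, gives three estimates and no test or interval for their difference. The bands will also differ in size, so the same true effect can be significant in one and not in another merely because one has more women.

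Two features of the bands add to this. The youngest runs only from the entry age of 16 to 19, in a disease whose average onset the protocol puts at 20 to 40, so few women may fall in it. The oldest is named for a reproductive stage that is not measured, in women who must have cycles of 23 to 36 days.

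At stake is a report that menstruation affects fatigue in one age group and not another when it does so equally in both, or that an over-40 finding reflects peri-menopause. The protocol hopes its results will help shape strategies for managing symptoms around the cycle, so such a claim could be taken up even though the analysis is exploratory.

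**Working it through.** The plan gives no size, effect, SD, alpha or power for any band, so it has no figure to reproduce. The check asks how often separate band analyses disagree when the true phase effect is the same at every age.

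**Inputs from the protocol**

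- Maximum 300 participants; 20% dropout anticipated: 300 × 0.80 = 240.
- In the cited pilot study, 47 of 70 enrolled women gave more than 4 weeks of data: 300 × 47/70 ≈ 201.
- Cut-points at 20 and 40; lower age limit 16.

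**Assumptions, not in the protocol**

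- Age is truncated normal on 16-52, mean 33-38, SD 7-8.
- Each band is tested with a two-sided 5% one-sample t-test on the within-woman difference (menstruation minus other phases).
- The true effect d, in SDs of that difference, is the same at all ages.

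**Step 1: band sizes.** Each band size is N times the probability of the band, rounded. With N = 201:

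| Mean, SD | Under 20 | 20-40 | Over 40 |
|---|---|---|---|
| 33, 7 | 5 | 165 | 32 |
| 33, 8 | 7 | 156 | 38 |
| 38, 7 | 1 | 125 | 75 |
| 38, 8 | 2 | 123 | 76 |

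**Step 2: disagreement between the two adult bands.** The bands contain different women, so the tests are independent. With powers p1 and p2, P(disagree) = p1(1 − p2) + p2(1 − p1).

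- d = 0: 2 × 0.05 × 0.95 = 0.095.
- d = 0.25, mean 33, SD 7: p1 = 0.891 and p2 = 0.278, so 0.891 × 0.722 + 0.278 × 0.109 = 0.67.
- d = 0.25, mean 38, SD 7: p1 = 0.792 and p2 = 0.570, so 0.792 × 0.430 + 0.570 × 0.208 = 0.46.

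Over the assumed age distributions:

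| True d, same at all ages | Adult bands disagree, N = 201 |
|---|---|
| 0 | about 10% |
| 0.1 | 28-29% |
| 0.20-0.25 | 46-67% |
| 0.3 | 31-62% |
| 0.5 | 1-22% |

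With N = 240, the figure at d = 0.20-0.25 is 39-66%.

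**Step 3: one interaction test instead.** This was simulated with 4,000 runs at N = 240, a common true effect, and assumed band shares of 2/58/40% or 5/55/40%. The false-positive rate was 4.9-5.1% with linear age and 4.6-4.7% with quadratic age.

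**Step 4: precision of the youngest band.** The 95% CI half-width, in SDs of the difference, is t(0.975, n − 1)/√n.

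- n = 5: 2.776/2.236 = 1.24
- n = 7: 2.447/2.646 = 0.92
- n = 24 (an assumed 10% of 240): 2.069/4.899 = 0.42, with 29% power at d = 0.3
- n = 201 (all women): 0.14

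**Step 5: which form of age.** Power of the interaction test in the same simulation:

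| True modification | Linear age | Quadratic age | Three groups (2 df) |
|---|---|---|---|
| 0.02 SD per year | 83-87% | 75-79% | 60-66% |
| Step of 0.4 SD at age 40 | 71% | 65-66% | 77-78% |
| U-shape | 5-7% | 64-65% | 16-18% |

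Continuous age does better for a gradient, and for a U-shape only if curvature is allowed. The three-group test does slightly better for a step exactly at 40.

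**The case against.** The plan says it will explore, and this is not the primary outcome. Three stronger readings are tempting, and the documents support none of them.

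- **That modification will be declared from significance in one band and not another.** The text states no such rule; comparing band estimates with their CIs fits it equally well. The disagreement rates therefore show what happens if the bands are read by significance. They also depend strongly on d, peaking near 0.20-0.25 and falling to 1-22% at 0.5, and the protocol gives no effect size.
- **That the youngest band will be nearly empty.** No age mix is given, and 16-19 year-olds, including mature minors, are deliberately eligible. A 10% share would give 24 of 240: sparse, not empty.
- **That the over-40 band is mislabelled.** Entry excludes women who have entered menopause, not those in peri-menopause. Cycles of 23 to 36 days do not show that these women are outside it. The documents support only that age stands in for a stage nobody verifies.

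The remedy also has limits. The question concerns reproductive stage, which continuous age does not fully represent, and a straight line can miss non-monotone modification. An interaction test still errs at about 5% for each of several outcomes.

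These objections narrow the point. They do not supply the missing comparison: even CIs reported band by band give no estimate of the difference between phase effects.

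**Conclusion.** The concern holds in a limited form. The plan names a method, stratification, that does not test the effect modification it sets out to explore, and the data for a better one are already collected. If bands are compared by significance, an identical effect would look different in the two adult bands in roughly half to two-thirds of studies at d = 0.20-0.25, and much less often at zero or large effects. The range rests on the assumed age distribution, the number evaluable and d. The lack of an interaction term does not depend on them.

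The under-20 band would hold about 1-7 of 201 women under these assumptions, and its own estimate would be imprecise even at a 10% share. The peri-menopause label is unverified, not shown to be wrong. Because the analysis is exploratory and secondary, this is a change the sponsor should make, not a threat to the primary result.

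**What to change.** - Pre-specify one phase-by-age interaction in a repeated-measures model, with age continuous and curvature allowed (a restricted cubic spline, not a straight line alone).
- Report the interaction test and the phase contrast with 95% CI at chosen ages, for example 20, 30, 40 and 45.
- If the sponsor wants to keep its categories, add a phase-by-age-group interaction.
- Present the three bands descriptively, with sizes, estimates and CIs, and draw no conclusion about effect modification from significance within a band.
- Label the last band as over 40, still cycling, or state that age is used as a proxy for peri-menopause.
- State that the analysis remains exploratory, and how many outcomes the interaction is tested on.

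The cost is wording in the Analytical Plan and a few extra degrees of freedom; no new data are needed. The test limits spurious age differences to about 5% per outcome and does not remove them across several outcomes.
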